5.2. Comparators

As of today mammography screening with 2D mammography is the global standard of care. Tomosynthesis is only recently approved for screening and is not reimbursed in many countries, and has no harmonized quality control procedure.

Also there are no established guidelines for Tomosynthesis in terms of angles, dose, number of slices required or how it should be used. Therefore this study uses 2D mammography as the comparator.

5.2.1. Maintenance and calibration

The system will be maintained and calibrated according to the systems manual.

5.3. Subjects

Subjects participating in the study will be selected based on the inclusion and exclusion criteria:

5.3.1. Inclusion criteria

- Patient is female and at least 40 years of age
- No contraindication for routine bilateral mammography

Philips Mammography Solutions Sweden	Clinical Investigation Plan Comparison of the Philips MicroDose Tomosynthesis System to 2D Digital Mammography	DOC-MTIN-9RWH8K- 8.0 Page 16 of 38
---	---	--

Screening Cohort

- Patient presents for a routine screening mammogram

Biopsy Cohort

- Patient is scheduled for a biopsy
- Patient has a screening detected abnormality

5.3.2. Exclusion criteria

- Patient is pregnant or believes she may be pregnant; OR,
- Patient is breast feeding; OR
- Patient is unable or unwilling to give informed consent, including consent to reuse data for future research; OR,
- Patient has breast implants; OR
- Patient has previous surgical biopsy; OR
- Patient has previous breast cancer; OR
- Patient presented to screening with clinical symptoms (e.g. palpable lump, nipple discharge, nipple retraction, skin irritation or dimpling)

5.3.3. Enrollment and duration

Subjects are considered to be enrolled in the study after they have signed the informed consent form. No study procedures will be performed before this moment.

The study period, per subject, is approximately up to 90 minutes and is limited to a single mammography session, except for the normal cases which will require a one-year follow-up exam (normal screening exam, not using the investigational device).

5.3.4. Number of Subjects and Readers

Approximately 800 patients who fulfill all inclusion and exclusion criteria and pass the quality control for completeness of image and patient information will be enrolled in the image accrual phase of the study. Among these patients approximately 300 normal, 65 cancer, and 40 biopsy-proven benign cases will be included in the image reading phase of the study.

The numbers of readers, and the overall sample size justification for the study is detailed in the Statistical considerations, section 6 of this protocol.

5.3.5. Procedure for the replacement of subjects

Subjects will not be replaced.

5.3.6. Subject withdrawal or discontinuation

Subjects can withdraw informed consent at any time during the trial.

5.4. Procedures

5.4.1. Image Accrual

The subjects will be recruited to either the biopsy cohort or the screening cohort as discussed in section 5.1. If the inclusion/exclusion criteria are met for either cohort, the subject will be asked to

Philips Mammography Solutions Sweden	Clinical Investigation Plan Comparison of the Philips MicroDose Tomosynthesis System to 2D Digital Mammography	DOC-MTIN-9RWH8K- 8.0 Page 17 of 38
---	---	--

participate in the study. The enrollment procedure will include study brief, inclusion/exclusion criteria, informed consent, randomization and data base entry (using a CRF). If the subject has no prior 2D screening exam, she will be randomized to either be imaged first on the investigational device and thereafter on the FFDM system, or the other way around. Imaging will be acquired by a trained technologist at site. Data management will be performed by a study assistant from each site; this includes anonymization, export, updated CRF etc.

5.4.2. Image Reading

The readers will independently review Philips MicroDose Tomosynthesis images and FFDM screening mammograms in two separate sessions using dedicated softcopy review workstations. The reading sessions will be separated by a wash-out period of at least one month. There will be equal numbers of cancer cases and equal mixture of FFDM and Tomosynthesis exams in each group.

Each reader will work at a designated workstation and will complete the case report forms independently. Readers will read in private reading rooms with very low ambient lighting. A study assistant will be available in the lab but not in the reading room to monitor each reader's progress and to resolve any issues that are unrelated to the actual image interpretation.

The review of Tomosynthesis will include reading of the Tomosynthesis (CC and MLO) plus synthesized 2D images (CC and MLO) generated from the tomosynthesis images. The review of FFDM exams will include reading the standard bilateral 2-view mammograms (CC and MLO). No patient history or other clinical information will be provided to the readers. Each reader will have a case lists displaying images in the prescribed order for each reader session.

The reader will review the images for a given modality then will follow the reporting workflow depending upon whether they would recall the patient or not based on the imaging data presented.

The Confidence Scores for recalled cases will have to fall between (51 and 100) and the confidence scores for the no recall cases will have to fall somewhere between (1 and 50). For the per-case ROC analysis, the confidence score for the case will be the overall score documented by the reader.

5.4.2.1. No Suspicious Findings (No Recall) Reporting

If the reader believes that a case contains no suspicious lesion(s), the reader will be asked to assign an overall forced BI-RADS® rating and a confidence score of the case being normal (1 to 50). The score 1 represents the least suspicious No-Recall case, whereas the score 50 represents the least suspicious No-Recall case. The allowed forced BI-RADS ratings are 1 and 2 for all cases that the radiologist interprets as containing NO suspicious, including benign lesion(s) that he or she is not recommending for additional imaging after screening.

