5.4.2.2. Suspicious Findings (Recall) Reporting

For each of the image sets, the reader will examine the images and look for any area of concern. For each suspicious lesion(s) triggering the need to recall a patient, the reader will localize the lesion(s) by providing the laterality and an o'clock location, assign a forced BI-RADS® rating, and the confidence score of the lesion being malignant (CS) (51 to 100) will be reported. The score 51 represents the least suspicious recall case, whereas the score 100 represents the most suspicious recall case. The reader will also provide the lesion type and size. After marking and rating all lesions, the reader will be asked to assign an overall BI-RADS® rating and CS score for the whole case. The allowed forced BI-RADS® ratings for suspicious lesion(s) are 3, 4, or 5. BI-RADS® 0 rating is not allowed in this study.

The annotations of suspicious lesion(s) will be made on the softcopy review workstation using the software features of case review application.

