5.5.2. Clinical Endpoint: Image Reading Phase

The Readers will independently review Philips MicroDose Tomosynthesis images and FFDM screening mammogram for each case in two separate reading sessions separated by a wash-out period of at least one month. The cases to be included in the reader study will be divided into two groups with an equal number of cancer cases and an equal number of FFDM and tomosynthesis exams in each group.

The review of FFDM exams will include reading the standard bilateral 2-view mammograms (CC and MLO). The review of Tomosynthesis will include reading of the Tomosynthesis (CC and MLO) plus synthesized 2D images (CC and MLO) generated from the tomosynthesis images. No patient history

Philips Mammography Solutions Sweden	Clinical Investigation Plan Comparison of the Philips MicroDose Tomosynthesis System to 2D Digital Mammography	DOC-MTIN-9RWH8K- 8.0 Page 23 of 38
---	---	--

or other clinical information will be provided to the Readers. The following data points will be collected using case report forms which will be completed directly by the readers:

- Forced BI-RADS score of 1, 2, 3, 4a, 4b, 4c, or 5
- Confidence Score (CS): Readers will be asked to assign a confidence score for the BI-RADS ratings as follows: For BI-RADS 3 to 5, the confidence score represents the reader's interpretation of the likelihood of the lesion being malignant on a scale of 51 to 100. The score 51 represents the least suspicious Recall case, whereas the score 100 represents the most suspicious Recall case. For BI-RADS 1 or 2, the confidence score represent the reader's confidence that the case is normal and will range from 1 to 50. The score 1 represents the most normal No-Recall case, whereas the score 50 represents the least normal No-Recall case. For the per-case ROC analysis, the confidence score for the case will be the overall score documented by the reader.
- Readers will mark all lesions by location (breast and clock location).

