6.6. Primary Efficacy Analysis

The primary objective of the study is to compare the clinical performance of the Philips MicroDose tomosynthesis system (tomosynthesis with a synthetic 2D) images and 2D FFDM system. The primary endpoint is the Area under the ROC curve (AUC) using patient as the unit of analysis. The ROC curves will be generated using the confidence scores (1 to 100) and the reference standard (i.e., normal/benign or cancer). All subjects with both Philips MicroDose tomosynthesis system and FFDM evaluation (modified intent to treat, MITT). For subjects with negative outcome for whom a 1 year follow-up is required, missing values will be removed from the study database.

Smooth ROC curves and area under the curve will be estimated from the CS for each study reader interpreting images acquired with the Philips MicroDose tomosynthesis system and the FFDM

Philips Mammography Solutions Sweden	Clinical Investigation Plan Comparison of the Philips MicroDose Tomosynthesis System to 2D Digital Mammography	DOC-MTIN-9RWH8K- 8.0 Page 29 of 38
---	---	--

systems. If smooth ROC curves cannot be fitted for each reader in each condition (e.g., if there is perfect performance), nonparametric methods may be used. Results will be summarized across readers using the method of [10] which includes random effects for study readers and uses the jackknife to handle correlation within cases, as obtained in the corresponding OR-DBM MRMC software. Robustness of the statistical method may be explored through use of the ANOVA model of Obuchowski and Rockette [11]; this model includes random effects for study readers, and adjusts variances and hypothesis tests for correlations due to having each reader interpret the same case sample. The degrees of freedom may be adjusted as suggested by Hillis [14]. The average AUC for Philips MicroDose tomosynthesis system and the FFDM, the average difference between the two systems, and its standard error for use in computing confidence interval and to performing hypothesis tests for the difference will be estimated.

The following hypothesis will be evaluated:

- Null Hypothesis: $H_0: \Theta_2 - \Theta_1 \geq 0.05$
- Alternative Hypothesis: $\Theta_2 - \Theta_1 < 0.05$

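### The no-recall half (1 to 50) of the confidence scale has duplicate end anchors in 5.4.2.1 and a label in 5.4.2.1 and 5.5.2 that runs against the 5.5.2 anchors, so its direction is not securely fixed for the primary ROC analysis

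*Combined protocol and SAP*

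**What the plan says.** The overall per-case score is collected in two halves. Recalled cases score 51 to 100 and no-recall cases score 1 to 50 (5.4.2).

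- **Recall half, 5.4.2.2.** The direction is clear: "The score 51 represents the least suspicious recall case, whereas the score 100 represents the most suspicious recall case".
- **No-recall half, anchors in 5.4.2.1.** Both ends carry one label: "The score 1 represents the least suspicious No-Recall case, whereas the score 50 represents the least suspicious No-Recall case".
- **No-recall half, name in 5.4.2.1.** The reader assigns "a confidence score of the case being normal (1 to 50").
- **No-recall half, name in 5.5.2.** For BI-RADS 1 or 2, "the confidence score represent the reader's confidence that the case is normal and will range from 1 to 50".
- **No-recall half, anchors in 5.5.2.** "The score 1 represents the most normal No-Recall case, whereas the score 50 represents the least normal No-Recall case".
- **Use, 6.6.** "The ROC curves will be generated using the confidence scores (1 to 100) and the reference standard".

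Readers are trained on the confidence scales and receive written instructions (5.4.5.1). They then score 30 cases on their own, and a study assistant reviews their CRFs (5.4.5.2). During reading, a research associate checks for missing data and completeness (5.5.2).

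**The concern.** An ROC curve built from scores of 1 to 100 needs a higher score to mean more suspicion over the whole range. The recall half meets this. The no-recall half meets it only if the 5.5.2 anchors are followed. The name given to the score in both sections points the opposite way, and the 5.4.2.1 anchors give no direction because they are identical. Section 5.5.2 therefore does not cleanly repair 5.4.2.1, since its own name and anchors disagree. Nowhere do the documents say outright that 1 to 100 is one increasing suspicion scale.

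A reader who took the name at face value would give scores near 50 to the clearest normals. Those cases would then rank just below recalled cases and above missed cancers scored low. That reader's AUC would fall, and readers using different directions would not be comparable. A reversed score is complete and in range, so a completeness check would pass it. If the direction a reader used is not recorded, it cannot reliably be put right afterwards.

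**Working it through.** The plan gives no figure for the effect of the scale wording, so there is none to reproduce.

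**Step 1. Direction implied by each statement about 1 to 50**

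| Source | A higher score means |
|---|---|
| 5.4.2.1, name of score | more normal |
| 5.4.2.1, anchors | undetermined (1 and 50 labelled alike) |
| 5.5.2, name of score | more normal |
| 5.5.2, anchors | less normal |
| Continuity with 51 to 100 (5.4.2.2) and ROC use (6.6) | less normal |

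**Step 2. Inputs for the size**

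- Control AUC A = 0.85 (6.1.1).
- Non-cancer recall f = 0.438, the FFDM recall rate in 6.1.3.
- Alternative f = 1 − 0.70 = 0.30, from the specificity in 6.1.5. This is a proxy. Specificity is cut at BI-RADS 4 (4.2), while BI-RADS 3 also counts as recall (5.4.2.2), so 0.30 is a floor for recall under that specificity.
- Assumption: equal-variance binormal scores, with every no-recall score reversed.

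**Step 3. Formula**

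Let d = √2 × Φ⁻¹(0.85) = 1.466 and let the recall cut be t = Φ⁻¹(1 − f). Then:

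- T = Φ(t) × Φ(t − d) is the probability that a cancer and a non-cancer both fall in the no-recall half.
- C is the part of T in which the cancer ranks higher.
- Full reversal replaces C by T − C, so the loss is 2C − T. If 1 to 50 carried no usable order (all tied), the loss would be half of that.

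| f | T | C | Loss, 2C − T | AUC after reversal | Loss if tied |
|---|---|---|---|---|---|
| 0.438 | 0.0535 | 0.0371 | 0.021 | 0.829 | 0.010 |
| 0.388 | 0.0727 | 0.0510 | 0.029 | 0.821 | 0.015 |
| 0.30 | 0.1213 | 0.0869 | 0.052 | 0.798 | 0.026 |

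Simulation gave 0.830 at 0.438 and 0.798 at 0.30.

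**Step 4. Effect on the tested quantity, FFDM AUC minus tomosynthesis AUC averaged over readers**

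- All readers reverse in both modalities, with equal AUC and equal recall: shift 0.
- All readers reverse, AUC 0.85 in both, FFDM recall 0.438 and tomosynthesis recall 0.438 − 0.05 = 0.388 (the reduction considered in 6.1.3): 0.0293 − 0.0207 = 0.0086, about 0.009 against tomosynthesis.
- All readers reverse, recall equal, true AUCs 0.85 (FFDM) and 0.80 (tomosynthesis): the loss at 0.80 is 0.0281 (f = 0.438) or 0.0658 (f = 0.30). The 0.050 difference becomes 0.050 + 0.0281 − 0.0207 = 0.057, or 0.050 + 0.0658 − 0.0524 = 0.063.
- Readers reverse in one modality only, k of 18: k/18 × (0.021 to 0.052). For k = 6 this is 0.007 to 0.017. Nothing in the documents suggests a one-modality pattern, so this is only a bound.
- A reader reverses in one session only: each session holds one case group in each modality (5.4.3), so half of each modality's cases are affected. In simulation with AUC 0.85, both modalities fell to about 0.840 (f = 0.438) or 0.823 (f = 0.30), and the mean shift in the difference was zero within simulation error.

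**The case against.** The strongest reply is that 5.4.2.1 contains a one-word slip. The sentence sets up a contrast, the 5.5.2 anchors supply the missing end, and a score of 50 sits next to 51 on a rising scale. Training on the scales, with a practice set and CRF review, is a condition of being a valid reader (5.4.4, 5.4.5). The CRF, workstation prompt and training text are not in the documents and may already be correct.

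Most of this stands. The intended direction is recoverable, and any AUC loss depends on a reader misreading the scale. But correcting the one word would leave the normality label in both sections, still opposed to the anchors. The training text does not say which direction is taught, and the Part 2 review is described as a check of CRF completion and understanding of the process, not of score direction.

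Three stronger readings are tempting and are not supported:

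- **That following 5.4.2.1 literally reverses the scale.** Its anchor for 1 agrees with the intended order, while its anchor for 50 and its label do not. The section is indeterminate, and reversal is one possible reading.
- **That a loss of 0.02 to 0.05 uses up the 0.05 margin.** The loss is one reader's absolute AUC under full reversal. The margin applies to the reader-averaged paired difference (6.6), where consistent reversal largely cancels.
- **That a change of direction between sessions enters the modality difference directly.** The crossover in 5.4.3 balances session against modality, so the result is noise and two lowered AUCs, with no systematic shift.

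**Conclusion.** The defect holds as an inconsistency in an operative scoring rule that feeds the primary endpoint: identical anchors in 5.4.2.1, and a label in 5.4.2.1 and 5.5.2 that contradicts the 5.5.2 anchors. Its consequence is conditional. The 0.021 loss rests on the protocol's own recall figure. The 0.05 end rests on the specificity proxy and is the less likely one. Both assume a binormal reader who reverses every no-recall score, and the documents give no basis for saying how many readers would.

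The realistic harm is added between-reader and within-reader noise, lowered reader and average AUCs in the report, and a small shift in the tested difference when recall or AUC differs between modalities: about 0.009 in the recall example, and 0.007 to 0.013 when the true AUCs are 0.85 and 0.80, in each case with all readers reversing. It should be corrected before reading starts, but it does not by itself put the non-inferiority conclusion in doubt.

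**What to change.** 1. In 5.4.2.1 and 5.5.2, define the 1 to 50 score as level of suspicion: 1 is the least suspicious (most normal) no-recall case and 50 the most suspicious (least normal) no-recall case.
2. Delete the description of the score as confidence that the case is normal from both sections.
3. State in 5.4.2, and again in 6.6, that 1 to 100 is one scale increasing with suspicion.
4. Use the same wording on the CRF, the workstation prompt and the written training instructions.
5. Add to the existing Part 2 CRF review (5.4.5.2) a check that each reader uses the low half in that direction, and record the result.

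The cost is a wording amendment and one extra item in a review that is already planned. No cases, readers or reading sessions are added.

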5.4.2.2. Suspicious Findings (Recall) Reporting

For each of the image sets, the reader will examine the images and look for any area of concern. For each suspicious lesion(s) triggering the need to recall a patient, the reader will localize the lesion(s) by providing the laterality and an o'clock location, assign a forced BI-RADS® rating, and the confidence score of the lesion being malignant (CS) (51 to 100) will be reported. The score 51 represents the least suspicious recall case, whereas the score 100 represents the most suspicious recall case. The reader will also provide the lesion type and size. After marking and rating all lesions, the reader will be asked to assign an overall BI-RADS® rating and CS score for the whole case. The allowed forced BI-RADS® ratings for suspicious lesion(s) are 3, 4, or 5. BI-RADS® 0 rating is not allowed in this study.

The annotations of suspicious lesion(s) will be made on the softcopy review workstation using the software features of case review application.

5.4.2.3. Matching Reader Indicated Lesion Locations to Truth

For all cancer cases, the lesion location(s) provided by the readers will be assessed for correspondence to the known cancer locations. For purposes of analysis, the cases which the reader assigns a score of BI-RADS 3 or higher and which correspond to the known cancer location (as described below) will be considered as correctly localized.

5.4.2.4. Correct Localization:

A reader will get credit for correct localization of a cancerous lesion if the laterality matches the true laterality of the cancer and any of the three rules below apply:

- Reader recorded lesion at a specific o'clock location anywhere from 1 to 12 is the same as the o'clock location documented by the truther within 2 o'clock ticks.
- Lesions indicated by the truther as being located in the Subareolar region that is reported as Subareolar by the reader.
- Lesions indicated by the truther as in the Axillary Tail region must be reported in either the Axillary Tail or 10, 11, or 12 o'clock (right breast) or 12, 1, 2 (left breast) by the reader.

5.4.3. **Case selection - Image Reading**

Cases for the reader study will be selected from all of the cases acquired through the case acquisition phase. A total of approximately 65 cancers, 40 cases with benign biopsies and 300 normal cases will be selected in sequential order to fulfill the requirements for case stratification. The 300 normal cases will include some cases that were recalled from screening but ultimately determined to be normal after additional work-up, as well as cases that were not recalled from screening. Approximately 10% additional cases will be included to protect from loss to follow-up prior to 1 year status verification.

Case stratification is described in detail in 5.4.6. In summary, cancer cases will be stratified by lesion type and size, and breast density. Benign cases will be stratified by lesion type and breast density. Normal cases will be stratified by breast density and by the recommendation for additional work-up after screening. Once the target case number is reached data collection will stop.

Approximately 18 American Board of Radiology (ABR) certified and Mammography Quality Safety Act (MQSA) qualified radiologists will review and score the cases according to Image Review methods described Image Reading, Section 5.4.2. All readers will undergo training on interpretation using the Philips MicroDose tomosynthesis system images to become familiar with the images and the review workstation to be used in the study.

To avoid recall bias, the reading will be divided in two sessions structured using a crossover design with a washout period of one month between sessions as presented in Figure 3.

[figure not shown]

Figure 3: Reading Scheme

Philips Mammography Solutions Sweden	Clinical Investigation Plan Comparison of the Philips MicroDose Tomosynthesis System to 2D Digital Mammography	DOC-MTIN-9RWH8K- 8.0 Page 19 of 38
---	---	--

Each reader will independently review 2D mammograms and MicroDose images (i.e., Tomosynthesis and synthetic 2D) of the same patient in separate sessions to minimize memory effects. The cases will be randomly divided into two groups, Group A and Group B. In the first reading session, the readers will read Group A with modality 1 and Group B with modality 2. In the second reading session, the readers will read Group A with modality 2 and Group B with modality 1. Within each reading session, the order in which the cases will be read will be randomized to avoid confounding the device effect with reading order effects.

Each reading session may be divided into several visit times to adapt to the readers' schedule. Furthermore, to avoid bias, no patient history or other clinical information will be provided to the reader.

